APPENDIX 5: AUDIT OF COMPLIANCE ADDED 17th July 2017

An audit of compliance with the affirm management protocol (appendix 4: updated 09/01/2015) for women presenting with reduced fetal movements will be determined by two means:

A) **QUESTIONNAIRE** Via Telephone or email contact with Principal Investigators at each site to determine which aspects of the AFFIRM protocol have been implemented effectively.

This will involve email contact with Principal Investigators to alert them to the request for information, detailing the information required, followed by a phone call to elicit the information (unless it had already been supplied). Investigators will be asked which of the following elements they had implemented locally:

- Issuing leaflets to all pregnant women,
- Cardiotocography within 2 hours of presentation,
- Measurement of amniotic fluid volume within 12 hours of presentation,
- Growth scan by the next working day for all women presenting with reduced fetal movement (and who had not had a growth scan within the last three weeks, or who were not being induced within 48 hours),
- Induction of labour within 48 hours for women presenting with recurrent reduced fetal movement at or after 37 weeks gestation.

Compliance (effective implementation) will be defined as 4/5 of the above management elements for 80% or more of the time.

AUDIT PART A: STAFF QUESTIONNAIRE

Dear (PI Name)

You very kindly agreed to answer some questions regarding your unit's compliance with the AFFIRM audit. We would be most grateful to receive your views on the following:

1. In your opinion, were the following aspects of the AFFIRM audit implemented at least 80% of the time at [Insert site name]?

Unit name: (Hospital name)	Yes	Partially	No	If Partially or NO, What proportion of women do you estimate received these?
Leaflets about RFM issued to women				
eLearning completed by staff				
CTG within 2 hours of presentation with RFM				
Growth scans for RFM (next working day)				
IOL for women 37 weeks and above with recurrent RFM (within 48hrs)				

2. If you could turn back time to 1st January 2014, and (with the benefit of experience) would you agree to participate in the AFFIRM study again? YES/NO

If NO, please could you explain why not?

We would be most grateful to receive your answers by **XX/ XXX/XXXX** If you haven't already given us your best address for sending out your vouchers, please don't forget to include this.

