As always, thank you so much for your help with AFFIRM.

Best Wishes

[name] and [name]
On behalf of the AFFIRM Study

NB: If you wish to print and fax your completed sheet to us, the number is [name]

B) **CLINICAL AUDIT** to determine whether the perception of the site Principal Investigator is supported by review of actual decision making will be performed for the following elements:

- Cardiocography within 2 hours of presentation,
- Measurement of amniotic fluid volume within 12 hours of presentation,
- Growth scan by the next working day for all women presenting with reduced fetal movement (and who had not had a growth scan within the last three weeks, or who were not being induced within 48 hours),
- Induction of labour within 48 hours for women presenting with recurrent reduced fetal movement at or after 37 weeks gestation.

This will be conducted by asking sites to complete an audit of the management of all women presenting with reduced fetal movement over the course of one calendar month. Sites will be asked to complete an audit form for each participant.

The audit form template (see below) has been generated by the central AFFIRM study team; anonymized forms will be analysed centrally. There will not be an attempt to corroborate Principal Investigator perception of the proportion of women who were given leaflets, nor will there be any attempt to incorporate the proportion of staff who had completed the e-learning package into analysis of whether any specific site has implemented the intervention or not.

AUDIT PART B: CLINICAL AUDIT FORM - One month data collection AUDIT [Month & Year] Unit name: [Name of Hospital]

If you assess a woman with reduced fetal movements (RFM), please complete the questions below. Do not worry if the woman has been seen in other areas of the hospital by other staff, we would rather have multiple reports for the same woman than miss episodes of RFM.

INSERT Patient Sticker (or WRITE name and CHI /NHS number)				AREA WHERE SEEN (CIRCLE)						
				Triage / Labour ward / Day Assessment Unit (DAU)						
				Other (specify area i.e. antenatal ward): _____						
Date and time of presentation with reduced fetal movements.	DATE: ____/____/____ TIME ____:____ am / pm			GESTATION AND EDD:	____ WEEKS ____ DAYS EDD: _____					
Referred by (TICK BOX):	Self	Community Midwife	GP	ANC	Triage	DAU	Other (specify: _____)			

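### The Part A compliance questionnaire omits amniotic fluid volume, one of the five elements in the 4/5 rule, and the induction element is worded as induction given although Appendix 4 asks for an offer

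*Protocol*

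**What the plan says.** Appendix 5 of the Protocol audits each site against the Appendix 4 management plan. It says that compliance "will be determined by two means": a questionnaire to each site's principal investigator (Part A) and a one-month clinical audit (Part B).

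Under Part A it lists five elements and gives the scoring rule: "Compliance (effective implementation) will be defined as 4/5 of the above management elements for 80% or more of the time". The third element is "Measurement of amniotic fluid volume within 12 hours of presentation". The fifth is induction within 48 hours for women with recurrent reduced movements at or after 37 weeks. Investigators are contacted by email setting out what is needed, "followed by a phone call to elicit the information (unless it had already been supplied").

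The printed Part A form has five rows: leaflets, "eLearning completed by staff", CTG, growth scan and induction. Each is answered yes, partially or no against an 80% standard. For partial or negative answers a further column asks, "What proportion of women do you estimate received these".

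Part B covers CTG, fluid volume, growth scan and induction, and its purpose is "to determine whether the perception of the site Principal Investigator is supported by review of actual decision making". On the first element the text says: "There will not be an attempt to corroborate Principal Investigator perception of the proportion of women who were given leaflets". It adds that eLearning completion will not enter the judgement of whether a site implemented the intervention. The Part B form records liquor volume with date and time, and asks whether induction was offered.

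For recurrent reduced movements at 37 weeks or later, Appendix 4 item iv tells units to offer delivery, within 48 hours, if the woman wants it.

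**The concern.** The rule counts five elements, but the form that accompanies it collects four of them. Its fifth row is an item that the rule does not use. A returned form therefore looks complete while lacking one scored element, and for some sites that element decides the result.

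The induction element raises a different problem. The audit is meant to show whether a unit followed Appendix 4, and Appendix 4 is satisfied by an offer. The element as written counts inductions. A unit can follow the plan in every case and still miss the element because women declined.

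Appendix 5 is the only place that defines effective implementation of the management plan at a site. Readers will use the audit to judge whether the package was delivered. If scoring is left to be settled when the replies come in, it may be settled with the results in view.

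**Working it through.** The plan gives no figure for this rule to reproduce, so the check compares the list with the form and then counts.

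**1. List against forms**

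| Element in the 4/5 rule | Row on Part A form | Field on Part B form |
|---|---|---|
| Leaflets | yes | yes, but not to be used to corroborate Part A |
| CTG within 2 hours | yes | yes |
| Amniotic fluid volume within 12 hours | **no** | yes |
| Growth scan next working day | yes | yes |
| Induction within 48 hours | yes, as induction | yes, as an offer |
| (eLearning, not in the rule) | yes, unscored | no |

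**2. What the Part A form can decide**

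Let m be the number of scored Part A rows met (0 to 4), and let f be 1 if fluid volume is met and 0 if not. The score is m + f, and compliance needs m + f ≥ 4.

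- m = 4: the score is 4 or 5, so the site is compliant whatever f is. Patterns: 1.
- m = 3: the score is 3 or 4, so f alone decides. Patterns: 4.
- m ≤ 2: the score is at most 3, so the site is non-compliant whatever f is. Patterns: 6 + 4 + 1 = 11.

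The total is 1 + 4 + 11 = 16, so 4 of 16 patterns are undetermined from the form. This counts patterns. It does not estimate the share of sites, because the documents give no element-level compliance rates.

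**3. Induction given against induction offered**

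Let o be the proportion of eligible women offered induction and a the proportion of those who accept. The proportion induced is o × a. Acceptance rates are not in the documents, so the values of o and a here are assumptions.

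- o = 1.00: o × a falls below 0.80 when a < 0.80, that is, when more than 20% decline. For example, a = 0.85 gives 0.85 (met) and a = 0.75 gives 0.75 (missed).
- o = 0.90: o × a falls below 0.80 when a < 0.80 / 0.90 = 0.889. For example, a = 0.90 gives 0.81 (met) and a = 0.85 gives 0.765 (missed).

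Scored as an offer, both units meet the element at any acceptance rate, because 1.00 and 0.90 both exceed 0.80.

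**4. How the two meet**

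Missing induction alone does not make a site non-compliant, since 4 of 5 is enough. But a unit that meets leaflets, CTG and growth scan and misses induction only because women declined has m = 3. That is one of the four patterns in which the missing fluid-volume answer decides the result.

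**The case against.** The strongest reply is that the procedure already covers fluid volume. The text says investigators will be asked about the listed elements, and the call is waived only if the information has been supplied. A form without fluid volume has not supplied it, so the call is still due. Part B also records it. This stands: the value is recoverable, and the 4-of-16 count describes the form on its own. What remains is that recovery depends on someone noticing that a fully completed form is one element short.

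On induction, the column about what women received applies only to partial or negative answers. Its heading also covers eLearning, which women do not receive, so it cannot bear much weight. The audit is of compliance with Appendix 4, under which a declined offer complies, and no sentence calls a refusal a failure. This weakens the point but does not remove it. The scored element and the Part A row both name induction, the Part B form asks about an offer, and no sentence says which counts.

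Three stronger readings are tempting, and the documents do not support them.

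- A reader might infer that neither part could ever cover all five elements. The Part B form does have a leaflet question. Not using it to corroborate Part A is a stated choice.
- A reader might infer that the two parts compete with no order between them. The 4/5 definition sits under Part A and Part B is described as a check on it, so the natural reading is that A classifies and B verifies. A sentence on what happens when they disagree would be an optional clarification.
- A reader might infer that the 80% threshold is to be applied to the few recurrent cases in one month of Part B data. No text says so.

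**Conclusion.** The point holds as a minor defect in an audit instrument and in the wording of one element. The Part A form omits one of the five scored elements and includes one unscored item. It leaves 4 of 16 response patterns undetermined unless the call or Part B supplies fluid volume. The induction element, read literally, can mark a unit that fully followed Appendix 4 as missing it once more than 20% of women decline. That changes the site's classification only if another element is also missed.

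The first part rests on comparing the printed form with the list. The form's table reads as intact, so the missing row does not look like a loss in text extraction. The second part rests on the literal wording, and since no decline rate is given, no probability of misclassification is claimed.

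A reader might infer that the trial's effect estimates are at risk. They are not. SAP 9.5 analyses stillbirth by intention to treat without this rule. The on-treatment variable in SAP 9.4, used in 9.5.1, groups women by when the intervention was actually implemented at the site. SAP 9.4 does not cite the 4/5 rule.

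**What to change.** 1. Add a row to the Part A form for amniotic fluid volume within 12 hours, and label the eLearning row as not scored.
2. Define the induction element, in the list and in both parts, as delivery offered within 48 hours, and state that an offer the woman declines counts as met.
3. Optionally, add one sentence saying that Part A classifies the site, what is done if Part B disagrees, and whether Part B may supply fluid volume when Part A lacks it.

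The cost is one new row, one relabelled row, one reworded element and a sentence or two of scoring rule. Part B already records fluid volume and whether induction was offered. Its date field refers to the induction itself, so a box for a declined offer would make the offer-based score clean. Sites that have already returned Part A need one follow-up question on fluid volume, plus a check of any partial or negative induction answer to see whether it reflects refusals.

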**Document Version History**

Version Number	Reason for Update	Updated By:	Date
0.00	Creation of new statistical analysis plan	[name]	22 Feb 2016
0.01	Comments from Trial Statistician incorporated	[name]	26 Feb 2016
0.02	Comment from study team incorporated	[name]	04 Apr 2016
0.03	Comment from Study team incorporated	[name]	30 May 2016
1.00	Further comments from Trial Statistician incorporated	[name]	27 Sep 2016
1.01	Final comments from study team incorporated	[name]	04 Oct 2016
2.0	Amendments following Trial Steering Committee December 2016	[name], [name]	30 March 2017
3.0	Updates to account for missing data patterns in covariates, based on review of data blinded to randomised allocations	[name]	03 October 2017

## 2 List of Abbreviations

AE	Adverse event
CEMACH	Confidential Enquiries into Maternal and Child Health
CI	Confidence interval
CONSORT	CONsolidated Standards of Reporting Trials
ECTU	Edinburgh Clinical Trials Unit
eDRIS	electronic Data Research and Innovation Service
ISA	International Stillbirth Alliance
ITT	Intention-to-treat
Max	Maximum
Min	Minimum
n	Number of patients with an observation
N	Number of patients in the dataset
PP	Per -protocol
Q1 , Q3	Inter quartile points at 25% and 75%
SAP	Statistical Analysis Plan
SD	standard deviation
SFTP	Secure File Transfer Protocol
SOP	Standard Operating Procedure
WHO	World Health Organisation

## 3 Introduction

This document details the criteria to be used for the definition of the analysis populations and the statistical methodology for analysis of the AFFIRM study. This document has been compiled according to Edinburgh Clinical Trials Unit (ECTU) standard operating procedure (SOP) “Statistical and Analysis Plans”. This document has been written based on information contained in the study protocol dated 27 February 2017 version 6.

### 3.1 Responsibilities

The trial statistician will be responsible for the production of the following items using ECTU SOPs: summary tables, formal statistical analysis and the statistical report.

Economics analysis is an out of scope activity for this SAP.

The nested qualitative study examining the acceptability of the intervention to patients and health care providers and identify process issues (barriers to implementation) is also an out of scope activity for this SAP.

### 3.2 Definitions

Throughout the reporting of the study, the studied interventions will be reported as “Active Phase” and “Control Phase”, and will be collectively referred to as the Intervention groups.

Study time periods in this step wedge design will be defined as period 1 (1 to 4 months), period 2 (5 to 8 months), etc., until period 9 (33 to 36 months)

Two calendar months will be manually determined once the date for “Active Phase” and “Control Phase” are provided by the study team (i.e. for the 28 February 2015, two calendar months later will be 28 April 2015).

For all data, where applicable clinical visits/observations will be referred to as: delivery, 7 days post-delivery, between 7 days and 28 post-delivery and between 28 days and 1 year post-delivery.

## 4 Study Design

### 4.1 Brief Description

AFFIRM is a pragmatic, multi-centre, stepped wedge cluster design trial, in which participating hospitals in the UK will be randomized to the timing of introduction of a care package. The tested intervention is a package of care consisting of a management plan for identification and delivery of the ‘at risk’ fetus, together with strategies for increasing pregnant women’s awareness of the need to report decreased fetal movements early.

Data in the ‘Active Phase’ after introduction of the intervention will be compared to data in the ‘Control Phase’. There will be a washout period of two calendar months after the introduction of the intervention commences during which data will not be included in either group for analysis. Outcomes will be measured from routinely collected data.

## 5 Research Outcomes:

### 5.1 Primary:

The study Primary Endpoint is:

- Stillbirth (antepartum and intrapartum). We will use the Confidential Enquiries into Maternal and Child Health (CEMACH) definition of stillbirth which is “a baby

delivered without signs of life after 23+6 weeks". Where gestation is uncertain we will include all babies with a birth weight of 500g or more.

## 5.2 Secondary:

The study secondary endpoints are:

- Stillbirth at 28 weeks gestation and above (World Health Organisation (WHO) definition of stillbirth: "a baby born with no signs of life at or after 28 weeks' gestation")
- Stillbirth at 22 weeks gestation and above: Delivery of dead fetus at or more than 22 weeks gestational age determined by weeks of pregnancy at delivery or gestational age at diagnosis of fetal death, if known; or birth weight of 500 grams or more, if fetal gestational age is not known.
- Stillbirth at 37 weeks gestation and above
- Stillbirth amongst normally formed infants of 22 weeks gestation and above, 24 weeks gestation and above, 28 weeks gestation and above and 37 weeks gestation and above (a normally formed infant is identified by the variable Fetal abnormality marker =No in the study dataset)
- Perinatal mortality (defined as stillbirth at 24 weeks gestation and above and deaths in the first seven days of life)
- Rates of caesarean section
- Rates of induction of labour (overall)
- Rates of elective delivery (induction of labour and caesarean section prior to the onset of labour) overall
- Rates of induction of labour at 39 weeks 0 days gestation or later
- Rates of elective delivery (induction of labour and caesarean section prior to the onset of labour) in women delivered at 39 weeks 0 days gestation or later
- Mean gestation at delivery for women having induction of labour
- Rates of admission to the neonatal unit (and their reasons)
- Rates of admission to the neonatal unit for more than 48 hours
- Rates of admission to the neonatal unit for term babies (those born at 37 weeks 0 days or greater)
- Birthweight centile (according to the Intergrowth birthweight centile calculator at <https://intergrowth21.tghn.org>)
- Proportion of babies with fetal growth restriction (defined as "being less than the 10th centile (customised for gender) and remaining undelivered at or after 40+0 weeks gestation)
- Rates of spontaneous vaginal delivery

Other secondary outcomes are the baby parameters:

- Gestation at delivery
- Proportion of babies born preterm ( $\leq 37$  weeks and 0 days gestation)
- Sex baby
- Birthweight of baby
- Birthweight centile (according to the Intergrowth birthweight centile calculator at <https://intergrowth21.tghn.org>)
- Apgar score at 5 minutes
- Proportion of babies with 5 minute Apgar score  $< 4$
- Proportion of babies with 5 minute Apgar score  $< 7$
- Resuscitation required at birth

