There is a clear association between maternal perception of decreased strength of fetal movement and late stillbirth. In a recent series of 2000 women, the adjusted OR (95% CI) of late stillbirth in women with decreased fetal movement (compared with controls) was 2.37 (1.29-4.35) (7). Although the mechanisms have not been fully delineated, it is likely that decreased fetal movement and stillbirth are linked by a common pathology, that of placental dysfunction. There is good evidence linking placental dysfunction and decreased fetal movement. Women who have fewer fetal movements on ultrasound immediately prior to caesarean section are more likely to have umbilical cord gas measurements indicative of acidaemia, hypoxaemia, and hypercapnia, compared with controls (8). Applicant [name] has shown that women delivering within one week of an episode of decreased fetal movement show differences in placental structure and function, including greater signs of infarction (compared to those with normal fetal movements) (9). Additionally, in a series of over 2000

women (conducted by applicant [name]), the odds of fetal growth restriction (FGR, defined as being at less than the 10th centile for gestation adjusted birthweight) were greater in women with decreased fetal movement compared with controls, with adjusted OR of 1.6, 95% CI 1.1–2.2 (10). Taken together these data are strong evidence that placental dysfunction is associated with decreased fetal movement, and a causative pathway seems likely.

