2.1.2 Secondary Objectives

The secondary objectives are to answer the research questions:

Q2. What is the effect of the above intervention on rates of caesarean section and induction of labour?

Q3. What is the effect of the above intervention on rates of admission to the neonatal intensive care unit?

Q4. What is the effect of the above intervention on the proportion of women with fetal growth restriction remaining undelivered by 40 weeks gestation?

Q5. What is the acceptability of such a package of care to pregnant women and their health care providers?

Q6. What other process outcomes are influenced by the intervention, such as health care provider/patient interactions?

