2.2.2 Secondary Endpoints

Other measures of perinatal mortality including:

- Stillbirth at 28 weeks gestation and above (WHO definition of stillbirth)
- Stillbirth at 22 weeks gestation and above
- Stillbirth at 37 weeks gestation and above
- Stillbirths amongst normally formed infants of 22 weeks gestation and above, 24 weeks gestation and above, 28 weeks gestation and above and 37 weeks gestation and above
- Perinatal mortality (defined as stillbirth at 24 weeks gestation and above and deaths in the first seven days of life)
- Rates of caesarean section
- Rates of induction of labour (overall)
- Rates of elective delivery (induction of labour and caesarean section prior to the onset of labour) overall
- Rates of induction of labour at 39 weeks 0 days gestation or later
- Rates of elective delivery (induction of labour and caesarean section prior to the onset of labour) in women delivered at 39 weeks 0 days gestation or later
- Mean gestation at delivery for women having induction of labour

- Rates of admission to the neonatal unit (and their reasons)
- Rates of admission to the neonatal unit for more than 48 hours
- Rates of admission to the neonatal unit for term babies (those born at 37 weeks 0 days or greater)
- Proportion of women with fetal growth restriction (less than the 10th centile, customised for gender) remaining undelivered at or after 40 weeks gestation
- Rates of spontaneous vaginal delivery

Other secondary outcomes are the baby parameters:

- Gestation at delivery
- Proportion of babies born preterm (\leq 37 weeks and 0 days gestation)
- Sex baby
- Birthweight of baby
- Birthweight centile (according to the Intergrowth birthweight centile calculator at <https://intergrowth21.tghn.org>)
- Apgar score at 5 minutes
- Proportion of babies with 5 minute Apgar score $<$ 4
- Proportion of babies with 5 minute Apgar score $<$ 7
- Resuscitation required at birth

We will also collect the following data:

maternal age, maternity unit of delivery, birthweight, gestation of delivery, parity, gestation, sex, smoking (current and ever), maternal BMI, number of babies (one or more), ethnicity (to allow a customised birthweight centile to be generated), method of delivery, Scottish index of multiple deprivation (or other deprivation scores) (where available) other neonatal variables: Apgar score, resuscitation required at birth, encephalopathy etc.

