### **7.2 Data analysis**

The statistician at ECTU will perform the statistical programming and analysis to produce all summary tables and figures using the statistical packages SAS (v9.2 or a more recent version), IBM SPSS (version 19 or later) or R, whichever is the most appropriate to use in the National Safe Haven.

In general terms, categorical data will be presented using counts and percentages, whilst continuous variables will be presented using the mean, median, standard deviation (SD), minimum, maximum, inter quartile points at 25% and 75% (Q1 and Q3) and number of patients with an observation (n) in the statistical output,

All statistical tests will be 2-sided and will be performed using a 5% significance level, leading to 95% (2-sided) confidence intervals (CIs) and corresponding p-values, unless otherwise specified.

Distributional assumptions underlying the statistical analyses will be assessed by visual inspection of residual plots. Normality will be examined by normal probability plots. If the distributional assumptions for the parametric approach are not satisfied, further data transformation (for achieving Normality), or other suitable methods will be considered. This will be documented in the statistical results report together with the reasoning supporting the action taken, if applicable.

The Intent-to-treat (ITT) population will be used to summarise all data and all analyses unless otherwise specified.

For the main clinical paper, appropriate MS Word tables will be compiled using the statistical output generated at the National Safe Haven (Examples in Appendix 1)

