## **8 Population for Analysis**

### **8.1 Intent to treat population**

The intention-to-treat (ITT) population will include all babies of women delivering at one of the AFFIRM study maternity units for the duration of the study.

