### 9.5 Primary Outcome

The primary outcome will be summarised overall, and by study site and active/control periods expressed as a rate per 1000 live births. Number of stillbirths (CEMACH definition) will be analysed on an intention to treat basis, incorporating all patients in the ITT population for whom outcome data are available. The number of stillbirths will be compared before and after implementation of the Active intervention using a logistic regression generalised linear mixed model following the model structure described in Hussey and Hughes [3]. The effect of implementation of the Active intervention will be presented as an odds ratio and its 95% CI. The intervention groups will be ordered in such a way that an odds ratio of less than one corresponds to a benefit for Active Phase over Control Phase

The event rate  $\mu_{ij}$  in site  $i$ , study period  $j$  will be modelled in the linear component of the logistic regression as:

$$\mu + \alpha_i + \beta_j + \theta X_{ij}$$

where:  $\mu$  is the overall mean event rate on the logit scale;

$\alpha_i$  is a zero-mean random effect for site  $i$ ,  $\alpha_i \sim N(0, \tau^2)$ ;

$\beta_j$  is the fixed effect log-odds ratio for time period  $j$ , with  $\beta_1=0$  for identifiability;

$\theta$  is the fixed effect log-odds ratio for the intervention;

$X_{ij}$  is a (0/1) variable to indicate whether the intervention is implemented in site  $i$  during period  $j$ .

A site by intervention interaction random effect will be included in the model and retained if it is found to explain an important proportion of the variability in outcomes.

The patient-level covariate included will be maternal age and number of babies (one; more than one).

A secondary analysis adjusting for a full list of patient-level covariates will also be included (maternal age, parity, smoking status during pregnancy, maternal BMI, number of babies (one or more) and ethnicity). This will be performed as a complete-case analysis.

A further secondary analysis not adjusting for patient level covariates will also be performed.

Also, a Scotland only model will be generated with the patient-level covariates included in the primary analysis plus the deciles of deprivation.

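### SAP 5.2 builds being undelivered at 40+0 into the definition of growth restriction, so outcome 9.6.14 as written does not estimate protocol question Q4

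*SAP*

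**What the plan says.** Protocol 2.1.2 (Q4) asks about the intervention's effect on "the proportion of women with fetal growth restriction remaining undelivered by 40 weeks gestation". The matching endpoint in Protocol 2.2.2 is "Proportion of women with fetal growth restriction (less than the 10th centile, customised for gender) remaining undelivered at or after 40 weeks gestation". Its bracket closes after the centile condition, so being small defines the group and being undelivered is the event. Protocol 1.1 also defines growth restriction by centile alone: "FGR, defined as being at less than the 10th centile for gestation adjusted birthweight".

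SAP 5.2 relabels the outcome as a proportion of babies with growth restriction and defines that condition as "being less than the 10th centile (customised for gender) and remaining undelivered at or after 40+0 weeks gestation". SAP 9.6.14 repeats only the short label. The default population under SAP 7.2 is ITT: that "population will be used to summarise all data and all analyses unless otherwise specified". SAP 8.1 says this population "will include all babies of women delivering at one of the AFFIRM study maternity units". SAP 9.6 sends the outcome to the primary-outcome model, for which SAP 9.5 states: "The effect of implementation of the Active intervention will be presented as an odds ratio and its 95% CI".

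**The concern.** With both conditions inside the definition, an analyst working from the SAP has two literal options. If the analysis is restricted to growth restriction as SAP 5.2 defines it, every baby is an event and nothing can be estimated. If the ITT default is used, the outcome is the share of all babies that are both small and undelivered at 40+0. Only the second can be run, and it answers a different question from Q4.

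The all-babies denominator is therefore inferred, not stated. SAP 9.10 does not settle it: it words the quantity a third way, which can be read as the share of small babies among those undelivered at 40+0. The unit also moves from women to babies without comment.

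At stake is one of the listed secondary research questions, and one that bears directly on the package's aim of identifying and delivering the at-risk fetus. The choice of denominator affects the reported odds ratio. If the intervention alters how many babies are small, it can also decide whether an effect is seen at all.

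**Working it through.** The documents state no rate, effect size or power for this outcome, so there is no planned figure to reproduce. The base rates below are assumptions, shown over a range.

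**Notation.** p = share of babies below the 10th centile, taken as 5%, 10% and 15%. u = share of those babies undelivered at 40+0, taken as 20%, 30%, 40% and 50%. Q4 estimates u. The literal 9.6.14 estimates p × u.

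**1. Share of small babies constant, 10% relative fall in u.** The risk ratio is 0.90 for both measures, because p cancels. The odds ratios differ:

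- Q4: [0.9u/(1 − 0.9u)] ÷ [u/(1 − u)]
- Literal: [0.9pu/(1 − 0.9pu)] ÷ [pu/(1 − pu)]

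With p = 10% and u falling from 40% to 36%:

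- Q4: (0.36/0.64) ÷ (0.40/0.60) = 0.844
- Literal, 4.0% to 3.6% of all babies: (0.036/0.964) ÷ (0.040/0.960) = 0.896

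| | Q4 odds ratio | Literal odds ratio |
|---|---|---|
| u = 20%, p = 5% | 0.878 | 0.899 |
| u = 40%, p = 10% | 0.844 | 0.896 |
| u = 50%, p = 15% | 0.818 | 0.893 |

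**2. Share of small babies changes with the intervention.**

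- u fixed at 40%, p from 10% to 9%: Q4 odds ratio 1.00, literal 0.896. With p from 10% to 11%, the literal odds ratio is 1.105.
- u from 40% to 36%, p from 10% to 11.1%: Q4 odds ratio 0.844. The literal measure stays at about 4.0% (0.111 × 0.36), odds ratio 1.00.

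**3. Would such a shift be visible?** I used Hussey-Hughes weighted least squares with the protocol's layout: 24 equal hospital groups, three stepping per period, nine periods, and half of each group's first active period dropped for the two-month washout. The analysed total is the protocol's 300,000, treated as babies (or 300,000 × p for small babies only). Residual variance is rate × (1 − rate). The between-site SD is CV × rate, with CV assumed at 0.1 and varied from 0 to 0.333, the upper value being the protocol's figure for stillbirth.

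At p = 10%, u = 40% and CV 0.1, the SE is 0.123 percentage points among all babies and 0.997 points among small babies. A 10% relative fall is 0.4 points in the first (0.4/0.123, about 3.2 SE) and 4.0 points in the second (4.0/0.997, about 4.0 SE).

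Across the grid:

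| Change | Measure | CV | Shift in SE |
|---|---|---|---|
| p falls 10%, u fixed | literal | 0.1 | 1.76-4.40 |
| p falls 10%, u fixed | literal | 0 | 2.04-5.78 |
| p falls 10%, u fixed | literal | 0.333 | 1.54-4.25 |
| p falls 5%, u fixed | literal | 0.1 | 0.88-2.20 |
| p falls 2%, u fixed | literal | 0.1 | 0.35-0.88 |
| u falls 10%, p fixed | Q4 | 0.1 | 1.92-5.88 |

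A 10% relative fall in u with p fixed moves p × u by the same amount as a 10% fall in p, so the literal measure's signal for a true Q4 effect is also 1.76-4.40 SE at CV 0.1.

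**4. Secular change.** A linear trend in p common to all sites, put through the same model as expected cell means, adds 0.00 points to the intervention effect. The period effects absorb it. Only a change tied to the intervention distorts the literal measure.

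**The case against.** The strongest reply is that this is an evident drafting slip. The opening quotation mark in the SAP 5.2 definition is never closed. One literal reading is degenerate. The SAP introduction says "This document has been written based on information contained in the study protocol dated 27 February 2017 version 6", and SAP section 6 reproduces the protocol's commitment to analyse Q1-Q4. A sensible analyst would go back to the protocol. The headings in SAP 9.6 are also uneven about denominators: 9.6.10 and 9.6.13 name a subset, but 9.6.3 and 9.6.9 do not spell one out, so silence in 9.6.14 is weak evidence that all babies was meant. Much of this stands: the slip is plausible though not proven, and the all-babies reading is an inference. But those statements point back to Q4 without correcting the definition, and an analysis plan should not leave a denominator to be guessed.

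A second reply is that the effect is small or hypothetical. With a constant share of small babies, direction and risk ratio agree, and the odds ratios differ only because they depend on the base rate. A shift in the share of small babies is not shown to be likely, and a 2% shift would mostly go unseen. That is fair, and it limits the weight of the point. The mean-difference models in 9.7.2 and 9.7.3 would also help reveal a shift, although they do not report the proportion below the 10th centile.

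Third, the protocol's denominator is fixed by birthweight centile, which is measured after the intervention and is itself an outcome (9.7.3). The all-babies proportion avoids that conditioning. This is true and is a reason to report both, but the SAP does not present its wording as a deliberate choice.

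The change of unit is largely explained by SAP 8.1, which counts babies throughout; it needs only to be stated.

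**Conclusion.** The concern holds. SAP 5.2 as written conflicts with the protocol's own endpoint, and nothing in SAP 9.6 repairs it. For a 10% relative fall in Q4 the odds ratio is 0.82-0.88 under the protocol and 0.89-0.90 under the literal SAP reading. Without a change in the share of small babies, the two agree in direction and in risk ratio. With one, they can disagree on whether there is any effect.

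The sizes rest on assumed base rates and site variation, and the consequence rests on the all-babies reading. The wording conflict rests on neither. It affects one secondary outcome; the primary analysis is untouched. It should be corrected.

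**What to change.** In SAP 5.2 and 9.6.14, restore the protocol endpoint:

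- **Denominator:** those below the 10th sex-specific birthweight centile.
- **Event:** delivery at or after 40+0 weeks.
- **Unit:** state babies, which is the SAP's ITT unit and the level at which a centile is defined; or keep women, as in the protocol, with a rule for multiple births.
- **Labels:** rename 9.6.14 to match and align the wording in 9.10.
- **Supplementary measure:** report the proportion of all babies that are both small and undelivered at 40+0, to cover the possibility that the package changes who falls below the 10th centile.

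The cost is SAP wording and one extra model on variables already collected. It should be settled before the randomisation list is released to the analysing statistician (SAP 7.5). The denominator shrinks to about 15,000-45,000 (5-15% of 300,000), but no power is lost in these illustrations: at CV 0.1 a 10% relative fall in Q4 is 1.9-5.9 SE with the protocol denominator, against 1.8-4.4 SE among all babies. The remaining drawback is that the denominator is measured after the intervention, which is why the supplementary measure is needed.
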